#### **Unscheduled Visits**

- Unscheduled visits will not be included in summary tables except for determining the worst-case values.
- Unscheduled visits will not be included in figures.
- All unscheduled visits will be included in listings.

Descriptive Summary Statistics					
Continuous Data Refer to IDSL Statistical Principle 6.06.1					
Categorical Data	N, n, frequency, %				
Graphical Displays					
Refer to IDSL Statistical Principals 7.01 to 7.13.					

## 11.3.3. Reporting Standards for Pharmacokinetics

Pharmacokinetic Concentration Data						
Descriptive Summary	Refer to IDSL PK Display Standards.					
Statistics, Graphical	Refer to IDSL Statistical Principle 6.06.1.					
Displays and Listings	For continuous data:					
	
 
NQs at the beginning of a participant profile (i.e. before the first incidence of a measurable concentration) are deemed to be zero as it is assumed that in this circumstance no drug is yet measurable in the blood.
 
For NQs at the end of the participant profile (i.e. after the last incidence of a measurable concentration);
 
					
	
 
for individual plots and pharmacokinetic analyses these are dropped (set to missing) as they do not provide any useful information (and can erroneously indicate that absolutely no drug is present)
 
for summary statistics, these are set to 0 (to avoid skewing of the
 
					
	
 
summary statistics)
 
Individual NQs which fall between two measurable concentrations are set to missing (individual values of this nature are assumed to be an anomaly)
 
If two or more NQ values occur in succession between measurable concentrations, the profile will be deemed to have terminated at the last measurable concentration prior to these NQs. For the purpose of individual participant plots, these NQs will be set to 0, and the subsequent measurable concentrations will be retained. For the derivation of pharmacokinetic parameters, these NQs and any subsequent measurable concentrations will be omitted (set to missing).
 
Note: Concentration values will be imputed as per GUI_51487 for descriptive summary statistics/analysis and summarized graphical displays only.
 
					
Pharmacokinetic Para	ameter Data					
Descriptive Summary Statistics, Graphical Displays and Listings	N, n, arithmetic mean, 90% CI of arithmetic mean, geometric mean, 95% CI of geometric mean, SD, SD of logged data CV (%), and between-subject geometric coefficient of variation (CVb (%)) will be reported. $ \text{CV}_{\text{b}} \text{ ($\infty$)} = \sqrt{\left(\text{exp}(\text{SD}^2) - 1\right) * 100} $					

(SD = SD of Ln-Transformed data)

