Study intervention: Portia (0.03 mg EE/ 0.15 mg LNG)		Х	Х	Х	Х	Х	Х	Х	Х	Х	Х	Х	Х	Х					
Study intervention: GSK3640254 200 mg								Χ	Х	Х	Х	Х	Х	Х					
Trough PK sampling: EE and LNG						D9						Х	Х						PK sample collected before dosing.

Procedure	Check-in	I	Run-ir	1					Tre	eatmen	t					Wash	out 1		Notes
	D -4	D -3	D -2	D -1	D 1	D 2-9	D 10 	D 11	D 12	D 13	D 14-18	D 19	D 20	D 21	D 22	D 23	D 24 	D 25	
Serial PK sampling: EE and LNG							X	Х						X	X	X	X		PK samples will be collected predose and after dosing at 15 and 30 minutes and 1, 1.5, 2, 3, 4, 7, 12, and 24 hours relative to Day 10 dosing. The 24-hour post-dose sample should be taken prior to dosing on Day 11. PK samples will be collected predose and after dosing at 15 and 30 minutes and 1, 1.5, 2, 3, 4, 7, 12, 24, 48, and 72 hours relative to Day 21 dosing.
Trough PK sampling: GSK3640254												Χ	Χ						PK sample collected before dosing.
Serial PK sampling: GSK3640254														Х	Х	Х	X	Х	PK samples will be collected predose and after dosing at 1, 2, 2.5, 3, 3.5, 4, 4.5, 5, 6, 8, 12, 24, 48, 72, and 96 hours relative to Day 21 dosing.
PD sampling: LH, FSH, progesterone					Χ		Х	Х						Х	Х				Samples collected before dosing.
AE review		←====================================								====									
SAE review	←====	====	====	=====	====	=====	=====	====	====	=====	======	=====	=====	=====	=====	=====	=====	==>	

Procedure	Check-in		Run-ir	1		Treatment										Wasl	nout 1		Notes
	D -4	D -3	D -2	D -1	D 1	D 2-9	D 10 	D 11	D 12	D 13	D 14-18	D 19	D 20	D 21	D 22	D 23	D 24 	D 25	
Concomitant medication review	←====		=====		====	=====		====	====	=====	======	=====	====	=====	=====		=====	==>	

AE = adverse event; D = Day; C-SSRS = Columbia Suicide Severity Rating Scale; ECG = electrocardiogram; EE = ethinyl estradiol; FSH = follicle-stimulating hormone; LH = luteinizing hormone; LNG = levonorgestrel; PD = pharmacodynamic; PK = pharmacokinetic; SAE = serious adverse event.

- 1 Washout period refers to follow-up period. See 208135 Protocol Clarification dated 10-Jun-2019.
- 2 Assessments performed on Day 10 will be considered Baseline for GSK3640254 dosing.
- 3 Evaluations scheduled for Day 24 will also be performed for participants who discontinue early.

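### SAP 11.3.3 does not limit the successive-NQ rule to the declining phase, so a steady-state EE or LNG profile with a measurable predose value and NQs at 15 and 30 minutes would lose its post-dose curve (low priority)

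*SAP*

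**What the plan says.** SAP 11.3.3 handles NQ results according to where they fall in the profile.

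- Leading: "NQs at the beginning of a participant profile (i.e. before the first incidence of a measurable concentration) are deemed to be zero".
- Single, embedded: "Individual NQs which fall between two measurable concentrations are set to missing".
- Successive, embedded: "If two or more NQ values occur in succession between measurable concentrations, the profile will be deemed to have terminated at the last measurable concentration" before them. For parameters, "For the derivation of pharmacokinetic parameters, these NQs and any subsequent measurable concentrations will be omitted (set to missing"). For plots, "For the purpose of individual participant plots, these NQs will be set to 0, and the subsequent measurable concentrations will be retained".

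The sampling grid is in SAP 11.1.1, Table 2, under serial PK sampling for EE and LNG: "PK samples will be collected predose and after dosing at 15 and 30 minutes and 1, 1.5, 2, 3", then on to 24 hours on Day 10 and to 72 hours on Day 21. Section 2.2 sets the primary objective at steady state under fed conditions, and section 7.2.4 uses the predose samples as troughs to judge steady state. AUC(0-τ), Cτ and Cmax of EE and LNG are the primary parameters (sections 2.2 and 7.1.4.1). The SAP mentions an LLQ only as a dashed line on the concentration plots (section 11.9.8) and gives no value.

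**The concern.** Ending a profile at a run of embedded NQs is sensible on the falling limb. In a profile that starts from no drug, that is where such a run would normally lie. These profiles start from a trough instead, and the next two samples may precede absorption. A run of NQs can therefore sit between a measurable trough and the whole dosing-interval curve, and the rule makes no exception for that position.

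The rules also disagree with each other around this case. A predose value just below the LLQ makes all three early samples leading NQs, and the curve is kept. A predose value just above it loses the curve. The individual plot would still show the full curve while its parameters were missing.

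At stake are the primary parameters of the affected participant and her within-participant comparison of Treatment B with Treatment A. If the pattern occurred, the analyst would have to discard a usable curve or depart from the SAP on a primary endpoint after seeing the data.

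**Working it through.** The SAP gives no figure on this point to reproduce. The check has two parts.

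**1. What the rules do.** I applied them literally to the 0–24 h grid (0, 0.25, 0.5, 1, 1.5, 2, 3, 4, 7, 12, 24 h), with AUC by linear-up/log-down trapezoids as in section 7.1.1.2. The profile is invented, in LLQ units: 1.02, 0.98, 0.97, 2, 4, 5, 4.5, 3.8, 2.6, 1.8, 1.05.

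| Case | Values kept for parameters | AUC(0–24) | Cmax |
|---|---|---|---|
| All values used, no NQ rule | all | 50.9 | 5.0 |
| Predose 1.02; 15 and 30 min NQ | predose only | not estimable | 1.02 at most |
| Predose changed to 0.99 (also NQ) | all; first three set to 0 | 50.2 | 5.0 |
| 30 min changed to 1.01 (only 15 min NQ) | all except 15 min | 51.0 | 5.0 |

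In the second case Cτ, the 24 h value, is missing as well.

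**2. How likely the trigger is.** All inputs here are assumptions, because the SAP gives none of them.

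*Simple form.* Assume a constant level through 30 minutes and independent log-normal assay error. Let r = true trough/LLQ and p = Φ(−ln r / CV), the chance that one sample is NQ. The chance of measurable, NQ, NQ is (1 − p)p².

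- r = 1.0: p = 0.5, giving 0.5 × 0.25 = 12.5%.
- r = 1.1: CV 10% gives p = 0.170 and 2.4%; CV 20% gives p = 0.317 and 6.9%.
- r = 1.25: CV 10% gives p = 0.013 and 0.02%; CV 20% gives p = 0.132 and 1.5%.

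*Simulation.* One-compartment steady state, half-life 8–36 h, absorption rate 1.5/h, lag 0–0.75 h, assay CV 10%. With no new absorption, levels fall by 1 − 2^(−t/half-life): 0.5–2.1% by 15 minutes and 1.0–4.2% by 30 minutes. That small fall is why the trough must lie almost at the LLQ.

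| Trough/LLQ | Lag 0.5 h or more | Lag 0.25 h or less |
|---|---|---|
| 1.0 | 14–20% | 0–1.6% |
| 1.1 | 3–6% | 0–0.1% |
| 1.25 | below 0.1% | 0 |
| 1.5 or more | 0 | 0 |

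**What the sampling plan implies.** Table 2 schedules EE and LNG samples at 48 and 72 h after the Day 21 dose, and section 7.2 plans a half-life for both. If a 48 h sample is measurable, the 24 h trough is at least 2^(24/half-life) × LLQ. At an assumed 36 h half-life, the longest tried, this is 2^(24/36) = 1.6 × LLQ; a measurable 72 h sample implies 2^(48/36) = 2.5 × LLQ. Shorter half-lives imply more. At these levels the simulated trigger probability is zero.

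**The case against.** The strongest reply is that the pattern is an edge case which the design makes unlikely. Sampling to 72 hours makes sense only if drug is expected to be measurable well past the trough. If troughs did sit at the LLQ, widespread unquantifiable Cτ would be the larger problem. This stands as an argument about likelihood. It is an inference about expected levels, not a guarantee for every participant, and it does not correct the wording.

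A second reply points to safeguards. Parameters are derived as far as the data allow (section 7.1.1.2), the PK Parameter population needs evaluable parameters (section 4), and the statistical analysis needs well-defined profiles (section 7.1.4.1). These would probably keep a one-point profile out of the analysis, but they cannot restore its curve. Section 7.1.1.2 also relies on working practices, and section 11.3.3 on display standards, that are not at hand. Those might treat the predose sample separately; the SAP text does not.

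Three stronger readings are tempting, and the document supports none of them.

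- *NQs at 15 and 30 minutes alone end the profile.* They do not. The predose and a later sample must both be measurable.
- *The rule biases the Cmax ratio by a known amount.* With a peak-to-trough ratio of 5, one of n pairs entering with Cmax equal to trough in Treatment B would multiply the B/A ratio by exp(−ln 5 / n): 0.898 at n = 15 and 0.938 at n = 25. Both the ratio and n are assumed, and a one-point profile is more likely to be missing than to be analysed.
- *The loss falls mainly on Treatment B and hides a reduction.* The probability (1 − p)p² peaks at p = 2/3 (4/27 = 14.8%) and then falls, because a lower predose becomes NQ and the curve is kept. A Cmax replaced by the trough in Treatment B would also exaggerate a reduction, not hide one.

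**Conclusion.** The defect in the rule is real and needs no assumed LLQ: for one definite pattern, section 11.3.3 omits a usable steady-state curve from derivation of the primary parameters, while it keeps the same curve when the predose value is lower. The loss is confined to parameter derivation.

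The practical risk is small. Under the assumptions above, it needs a trough within roughly 10–25% of the LLQ and an absorption lag of about 30 minutes or more. The SAP does not show that any profile would meet these conditions, and the late sampling suggests that most would not. The expected consequence is an occasional lost profile. Neither a quantified bias nor a direction by treatment is established. This is a low-priority correction.

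**What to change.** In SAP 11.3.3, apply the successive-NQ termination rule only to samples after the observed Cmax of the dosing interval, with Cmax identified before the rule is applied. Add: for steady-state profiles, NQ values between a measurable predose sample and the first measurable post-dose concentration are set to missing for parameter derivation, and all later measurable concentrations are retained.

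In the invented profile this restores Cmax (5.0) and Cτ (1.05). The three segments from 0 to 1 h (0.250 + 0.244 + 0.743 = 1.236) become one trapezoid, (1.02 + 2)/2 = 1.51, so AUC(0–24) is 50.93 − 1.24 + 1.51 = 51.2, about 0.5% above the value from all samples.

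The cost is one or two sentences. No new data are needed, and profiles without successive NQs before the peak are handled as now.

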#### CONFIDENTIAL

Parameters Not Being Ln- Transformed	Tmax, λz, λz lower, λz upper, and λz no. of points.
Parameters Not Being Summarized	λz, λz lower, λz upper, and λz no. of points.
Listings	Include the first point, last point and number of points used in the determination of λz and Rsq_adjusted for listings.

## 11.4. Appendix 4: Derived and Transformed Data

#### 11.4.1. General

#### **Multiple Measurements at One Analysis Time Point**

- Mean of the measurements will be calculated and used in any derivation of summary statistics but if listed, all data will be presented.
- The worst finding/interpretation associated with multiple measurements as the finding/interpretation for that time point.
- Participants having both High and Low values for Normal Ranges at any post-baseline visit for safety parameters will be counted in both the High and Low categories of "Any visit post-baseline" row of related summary tables. This will also be applicable to relevant Potential Clinical Importance summary tables.

#### **Study Day**

- Calculated as the number of days from Dose Date on Day 1:
  - Assessment Date = Missing
    - → Study Day = Missing
  - Assessment Date < Dose Date on Day 1

    - → Study Day = Assessment Date –Dose Date on Day 1
  - Assessment Date >= Dose Date on Day 1
    - → Study Day = Assessment Date Dose Date on Day 1 + 1

#### **Period Day**

- Calculated as the number of days from First Dose Date for the respective period:
  - Assessment Date = Missing
    - → Period Day = Missing
  - Assessment Date < Dose Date on Day -3

    - → Period Day = Assessment Date Dose Date on Day -3
  - Dose Day on Day -3 <= Assessment Date < Dose Date on Day 1

    - → Period Day = Assessment Date Dose Date on Day -3 + 1
  - Dose Date on Day 1 <= Assessment Date < First Dose Date on Day 11

    - → Period Day = Assessment Date Dose Date on Day 1 + 1
  - Assessment Date >= First Dose Date on Day 11
    - → Period Day = Assessment Date First Dose Date on Day 11 + 1

#### 11.4.2. Study Population

#### Age

- GSK standard IDSL algorithms will be used for calculating age where birth date will be imputed as follows:
  - Any participant with a missing day will have this imputed as day '15'.
  - Any participant with a missing day and month will have this imputed as '30th June'.
- Birth date will be presented in listings as 'YYYY'.

#### **Body Mass Index (BMI)**

Calculated as Weight (kg) / [Height (m)]

### 11.4.3. Safety

#### **Adverse Events**

# **AEs of Special Interest**

• Adverse events of special interest include all AEs classified in the cardiovascular (per MedDRA) system organ class, seizure, and syncope.

## 12-Lead Electrocardiograms

# **QTcF** Interval

• QTcF interval will be collected on the eCRF. If QTcF interval is missing on the eCRF, the value in msec will be calculated using QT interval (msec) and heart rate (bpm as

$$QTCF = \frac{QT}{\sqrt[3]{60/Heart Rate}}$$

#### **QTcB Interval**

• QTcB interval in msec will be calculated using QT interval (msec) and heart rate (bpm) as

$$QTCB = \frac{QT}{\sqrt{60/Heart \ Rate}}$$

# 11.5. Appendix 5: Reporting Standards for Missing Data

# 11.5.1. Premature Withdrawals

Element	Reporting Detail
General	
 
Participant study completion (i.e. as specified in the protocol) was defined as the participant had completed all phases of the study including the final date on which data were or are expected to be collected.
 
Withdrawn participants were not replaced in the study.
 
All available data from participants who were withdrawn from the study will be listed and all available planned data will be included in summary tables and figures, unless otherwise specified.
 

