# 2.2. Study Objective(s) and Endpoint(s)

[figure not shown]
Objectives	Endpoints
Primary Objectives	Primary Endpoints
To assess the effect of GSK3640254 on the steady state PK of EE and LNG under fed conditions in healthy female participants	• AUC(0- $\tau$ ), Cmax, and C $\tau$ for EE and LNG
Secondary Objectives	Secondary Endpoints
To assess the effect of GSK3640254 on the PD of EE/LNG (suppression of ovulation as indicated by endogenous progesterone levels)	Serum progesterone levels
To assess the effect of GSK3640254 on LH and FSH	Serum FSH and LH levels
To characterize the steady state PK of GSK3640254 in the presence of EE/LNG	• AUC(0-τ), Cmax, Cτ, Tmax, and t1/2 for GSK3640254
To Characterize the steady state PK of EE/LNG alone and in the presence of GSK3640254	Tmax and t1/2 for EE and LNG
To assess the safety and tolerability of GSK3640254 and EE/LNG when given in combination in healthy female participants	Safety and tolerability parameters for AEs/SAEs, observed and change from baseline clinical laboratory assessments, ECGs, and vital sign measurements

AE = adverse event; AUC(0- $\tau$ ) = area under the plasma concentration-time curve from time 0 to the end of the dosing interval at steady state; Cmax = maximum observed concentration; C $\tau$  = Plasma concentration at the end of the dosing

Objectives	Endpoints

interval; ECG = electrocardiogram; EE = ethinyl estradiol; FSH = follicle-stimulating hormone; LH = luteinizing hormone; LNG = levonorgestrel; PD = pharmacodynamic; PK = pharmacokinetic; SAE = serious adverse event; t1/2 = apparent terminal phase half-life; Tmax = time of maximum observed concentration.

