### 4. ANALYSIS POPULATIONS

Population	Definition / Criteria	Analyses Evaluated
Screened	
 
All participants who signed the informed consent form
 
This population will be used for screen failure listing and summary
 
	Study Population
Safety	
 
All participants who received at least 1 dose of study medication.
 
This population will be used for all demographic, disposition (exclude screen failure), and safety listings, summaries, and figure
 
	

Study Population

Safety

Pharmacokinetic Concentration	
 
All participants who underwent plasma PK sampling and had evaluable PK assay results.
 
This population will be used for the PK concentration listings, summary tables, and plotting of concentration-time data.
 
	PK Concentration
Pharmacokinetic Parameter	
 
All participants who underwent plasma PK sampling and had evaluable PK parameters estimated.
 
This population will be used for PK parameter listings, summary tables, and statistical analysis tables.
 
	

PK Parameter

PK statistical analysis

Pharmacodynamic Concentration	
 
All participants who underwent plasma PD sampling and had evaluable PD assay results.
 
This population will be used for the PD concentration listings, summary tables, and figures.
 
	PD Concentration

Refer to Appendix 9: List of Data Displays which details the population used for each display.

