#### 7.2.4. Statistical Analyses / Methods

Details of the planned displays are provided in Appendix 9: List of Data Displays and statistical principles.

Unless otherwise specified, endpoints/variables defined in Section 7.2.1 will be summarized using descriptive statistics, graphically presented (where appropriate), and listed.

Secondary plasma PK parameters (Tmax and t1/2) will be estimated for EE and LNG (Treatments A and B) and secondary plasma PK parameters AUC(0- $\tau$ ), C $\tau$ , Cmax, Tmax, and t1/2 will be estimated for GSK3640254 (Treatment B). Summary statistics (arithmetic mean, geometric mean, median, SD, minimum, maximum, and coefficient of variation) for secondary plasma PK parameters of GSK3640254 and EE and LNG will be summarized by treatment.

Predose (trough) PK plasma concentrations (EE and LNG: Days 9, 10, 11 [Treatment A], 19 through 21 and the 24-hour post-Day 21 dose [Treatment B]; GSK3640254: Days 19 through 21 and the 24-hour post-Day 21 dose [Treatment B]) will be summarized using the PK Concentration Population and used to assess achievement of steady state.

Boxplots with overlaid individual values of primary plasma PK parameters for GSK3640254 will be produced for subjects categorized by ALT (ALT level within normal range, ALT value is greater than upper limit of normal [ULN] but less than or equal to 3 times the ULN, and ALT level is greater than 3 times the ULN) and whether subjects met liver stopping criteria. Similarly, boxplots with overlaid individual values of primary plasma PK parameters will be produced by treatment with data presented according to subject's progesterone level (progesterone level is less than or equal to 6.36 nmol/L and progesterone level is greater than to 6.36 nmol/L) and whether subjects met liver stopping criteria.

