## 8.4. Statistical Analysis / Methods

Details of the planned displays are provided in Appendix 9: List of Data Displays and will be based on GSK Data Standards and statistical principles.

Individual concentration-time profiles will be created for LH, FSH and progesterone. For each parameter, the profiles for both treatments will be overlaid on the same plot.

Actual values for serum LH, FSH, and progesterone levels will be listed and summarized by treatment using descriptive statistics; in addition, the mean value with the SD will be presented in a figure. The maximum LH and FSH concentration of each treatment period will be identified for each subject and listed with treatment and day and summarized by treatment.

For each parameter (LH, FSH, and progesterone), the concentrations will be plotted by treatment and timepoint using box-plots displaying the median, range, 25th and 75th percentiles. Maximum LH and FSH will be plotted within the same figure.

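### The effect of GSK3640254 on progesterone, LH and FSH is read from unpaired by-treatment summaries of all available data, so the two columns can differ because of who withdrew

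*SAP*

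**What the plan says.** Two secondary objectives in SAP Section 2.2 concern an effect on pharmacodynamics. One is "To assess the effect of GSK3640254 on the PD of EE/LNG (suppression of ovulation as indicated by endogenous progesterone levels"; the other concerns the effect on LH and FSH.

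Section 8.4 gives the analysis: "Actual values for serum LH, FSH, and progesterone levels will be listed and summarized by treatment using descriptive statistics". It adds mean (SD) figures, box-plots by treatment and timepoint, and each participant's maximum LH and FSH by treatment. It also plans individual profiles: "For each parameter, the profiles for both treatments will be overlaid on the same plot". Neither Section 8.4 nor Tables 4.1 and 4.2 in Section 11.9.9 includes a change from A to B.

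Section 4 defines the PD Concentration population as "All participants who underwent plasma PD sampling and had evaluable PD assay results", with no condition that both treatments be represented. Section 11.5.1 adds "Withdrawn participants were not replaced in the study" and "all available planned data will be included in summary tables and figures, unless otherwise specified". Nothing in Section 8.4 or the table list specifies otherwise for the hormones.

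The Time and Events Table (Section 11.1.1) places hormone samples on Days 1, 10, 11, 21 and 22.

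**The concern.** Section 2 describes a single-sequence study, so each participant is her own control. The primary AUC, Cmax and Cτ analysis uses this through a mixed model with participant as a random effect (Section 7.1.4.1). The hormone summaries do not.

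A participant who stops after the Day 10/11 samples and before Day 21 keeps her hormone values on Portia alone and has none from Days 21 and 22. Early leavers receive the Day 24 evaluations, but no hormone sample is scheduled on Day 24. Between those sampling days the loss is one-sided: the A column keeps people whom the B column lacks.

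Section 2.2 states an effect objective, and the only numerical summaries are the two columns, so a reader will set them side by side. If those who left had unusual hormone levels, the gap between the columns partly reflects that and not GSK3640254.

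**Working it through.** **The documents side by side.** Four statements together produce the imbalance: a fixed order (Section 2), a PD population without a both-treatment condition (Section 4), withdrawn participants' planned data kept and no replacement (Section 11.5.1), and by-treatment summaries with no paired quantity (Section 8.4, Tables 4.1 and 4.2).

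**No figure to reproduce.** The SAP states no sample size, withdrawal rate or hormone SD. The values below are assumptions, shown as ranges.

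**Formula.** Let d be the share of participants with A data who have no B data. With no drug effect:

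- A column mean = (1 − d) × mean of those who stay + d × mean of those who leave
- B column mean = mean of those who stay
- B − A = d × (mean of those who stay − mean of those who leave)

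Absolute size in SD units:

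| d | gap 0.25 SD | gap 0.5 SD | gap 1.0 SD |
|---|---|---|---|
| 5% | 0.013 | 0.025 | 0.05 |
| 10% | 0.025 | 0.05 | 0.10 |
| 20% | 0.05 | 0.10 | 0.20 |
| 30% | 0.075 | 0.15 | 0.30 |

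For example, 0.10 × 0.5 = 0.05 SD. If the gap is zero, the spurious difference is zero at any d.

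**Simulation check.** Assumptions: 20 participants, no drug effect, within-participant correlation 0.6, a tendency to leave correlated 0.5 with the participant's own level, 40,000 runs. Mean B − A in SD units, with the run-to-run SD in brackets:

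| Dropout | All available | Participants with both |
|---|---|---|
| 10% | −0.070 (0.213) | 0.000 (0.211) |
| 20% | −0.130 (0.225) | −0.001 (0.223) |
| 30% | −0.184 (0.244) | 0.001 (0.239) |

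Under this model, the set with both values removes the shift and loses no precision. At 10% dropout the shift is about a third of the sampling variation of the difference (0.070/0.213 = 0.33).

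**Which days match.** The Day 10 and Day 21 samples are both taken before the dose on the serial PK day. Day 11 predose is 24 hours after the Day 10 dose, and Day 22 is 24 hours after the Day 21 dose. Day 1 follows only the three run-in doses and has no counterpart in B.

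**Maxima.** Section 8.4 does not say to which treatment the Day 11 hormone sample belongs. If it belongs to A, as Section 7.2.4 has it for trough EE and LNG, A has three samples (Days 1, 10, 11) and B has two (Days 21, 22). Otherwise A has two and B has three. A plain difference of maxima would compare unequal numbers of samples.

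**The case against.** The strongest reply is that no PD contrast is planned: Section 8.4 has no test, interval, ratio or difference. Readers also have the overlaid individual profiles (Figure 4.1), participant-level listings of every hormone value and of the maxima (Listings 40 and 41), medians and quartiles (Figure 4.3), and listings of withdrawals and treatment discontinuations (Listings 1 and 2). All of this stands and limits the harm. None of it gives a within-person summary for an objective worded as an effect.

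The rule in Section 11.5.1 is also not wrong in itself. Keeping all available data is reasonable; the gap is that nothing paired accompanies it.

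A reader might infer more than the SAP supports:

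- *Every withdrawal removes B data, and B holds completers only.* Follow-up runs to Day 25. Someone who leaves after the Day 22 sample loses no hormone data, is not a completer, and still counts in B.
- *A large false effect is to be expected.* One can construct it: 19 participants at 1 nmol/L throughout and one at 20 nmol/L who leaves give an A mean of (19 × 1 + 20)/20 = 1.95 against 1.00 in B, an apparent fall of 49%. Nothing in the SAP makes this case likely. Such a value would lie above the 6.36 nmol/L progesterone cut-off used in the PK boxplots, stand out in the individual plot and listing, and barely move the median.
- *Tmax has the same defect.* The PK Parameter population ("All participants who underwent plasma PK sampling and had evaluable PK parameters estimated") likewise needs no data in both treatments, and Tmax falls under the statement that summary statistics "for secondary plasma PK parameters of GSK3640254 and EE and LNG will be summarized by treatment". But that objective is only to characterize PK, and Section 11.3.3 reports N and n, so unequal denominators would show.

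**Conclusion.** The point holds in a limited form. The SAP answers effect objectives for progesterone, LH and FSH with unpaired summaries whose columns may cover different people. The size is d times the gap between those who stay and those who leave: 0.013 to 0.30 SD over the assumed ranges, and 0.05 SD at 10% dropout with a 0.5 SD gap. It requires withdrawals between the Day 10/11 and Day 21 samples, and those participants must differ on the hormone. The SAP shows neither. The primary PK conclusion does not depend on these summaries.

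This is a worthwhile, inexpensive improvement and not a flaw that threatens the study. The paired summary is protected against differences in participants' stable levels, as in the simulation. It still describes only those who reach the Treatment B samples, and says nothing about the response of those who left because of it.

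**What to change.** Keep the all-available summaries and show n for each treatment and day.

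- **Table 4.1:** for each hormone, add the within-participant change on matched predose days, Day 21 minus Day 10 and Day 22 minus Day 11, in participants with both values of the pair. Summarise A and B in that same set. State in Section 8.4 that the Day 11 predose sample is a Treatment A value for this purpose.
- **Table 4.2:** if a paired maximum of LH or FSH is added, take it from the same number of samples in each treatment (Days 10 and 11 against Days 21 and 22).
- **Tables 3.7 and 3.9:** a median paired Tmax difference for EE and LNG is optional.

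No new data are needed. The cost is a few table rows and a paired n slightly smaller than that of the A column.
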